6.2.3.6 Is an important medical event

Any event that does not meet the above criteria, but that in the judgment of the investigator jeopardizes the patient, may be considered for reporting as a serious adverse event. The event may require medical or surgical intervention to prevent one of the outcomes listed in the definition of "Serious Adverse Event". For example: allergic bronchospasm requiring intensive treatment in an emergency room or at home; convulsions that may not result in hospitalization; development of drug abuse or drug dependency.

6.3 Steps to Determine If an Adverse Event Requires Expedited Reporting

Step 1: Identify the type of adverse event using the NCI Common Terminology Criteria for Adverse Events (CTCAE v4).

Step 2: Grade the adverse event using the NCI CTCAE v4.

Step 3: Determine whether the adverse event is related to the protocol therapy Attribution categories are as follows:

- Definite The AE is clearly related to the study treatment.
- Probable The AE is likely related to the study treatment.
- Possible The AE *may be related* to the study treatment.
- Unrelated The AE is clearly NOT related to the study treatment.

Note: This includes all events that occur within 30 days of the last dose of protocol treatment. Any event that occurs more than 30 days after the last dose of treatment and is attributed (possibly, probably, or definitely) to the agent(s) must also be reported accordingly.

Step 4: Determine the prior experience of the adverse event.

Expected events are those that have been previously identified as resulting from administration of the agent. An adverse event is considered unexpected, for expedited reporting purposes only, when either the type of event or the severity of the event is not listed in:

- the current known adverse events listed in the Agent Information Section of this protocol;
- the drug package insert;
- · the current Investigator's Brochure

6.4 Reporting Requirements for Adverse Events

6.4.1 Expedited Reporting

- The Principal Investigator must be notified within 24 hours of learning of any serious adverse events, regardless of attribution, occurring during the study or within 30 days of the last administration of the study drug.
- The IRB/PPHS must be notified within 5 business days of "any unanticipated problems involving risk to subjects or others" (UPR/UPIRSO).

The following events meet the definition of UPR

- a. Any new information that indicates a new or increased risk, or safety issue (e.g., interim analysis, safety monitoring report, publication, updated sponsor safety report), that indicates an unexpected change to the risk/benefit ratio for the research.
- An investigator brochure, package insert, or device labeling is revised to indicate an increase or magnitude of a previously known risk, or describes a new risk.
- c. Withdrawal, restriction, or modification of a marketed approval of a drug, device, or biologic used in research protocol
- d. Protocol deviation or violation that harmed subjects or others or that indicated subjects or others might be at increased risk of harm.
- Complaint of subject that indicates subjects or others might be at increased risk of harm or at risk of a new harm

- Any breach in confidentiality that may involve risk to the subject or others.
- g. Any harm experienced by a subject or other individual that in the opinion of the investigator is unexpected and at least probably related to the research procedures.

6.4.2 Routine Reporting

All other adverse events- such as those that are expected, or are unlikely or definitely not related to the study participation- are to be reported annually as part of regular data submission.

Those AEs that do not require expedited reporting are reported in routine study data submissions. Expected AEs such as Grade 1 and 2 Skin Reactions, AST/ALT elevation, Grades 1 and 2, nausea/vomiting will not be reported in an expedited fashion. If the subject has an elevated GGT at the time of study entry, but has normal ALT and AST, reporting will not be required unless the grade has increased by 2 levels.

6.5 Stopping Rules

If patients exhibit respiratory distress or serious allergic reaction following 5-ALA administration, their participation in the study will cease

Stopping rules for trial enrollment have been incorporated into the protocol based on liver function tests (LFTs). The extensive European experience with Gleolan® and fluorescence- guided tumor resection has shown that patients very commonly have a transient increase in their liver enzymes (>=1/10). Peak values occur between 7 and 14 days after administration. However, LFT increases can occur up to 6 weeks after administration. The liver toxicity data available from the Phase III European trial (Stummer 2006) has shown that after 6 weeks, the incidence of Grade 3 and Grade 4 events (>5-10x or >10x upper limit of normal) occur in less than 6% of patients for ALT/GPT, AST/GOT, and Gamma-GT (GGT) liver testing. Approximately 10% had Grade 3 or 4 elevations in GGT at 7 days; 5% had Grade 3 or 4 elevations in GGT at 6 weeks, and 1% had persistent ALT or AST elevations at 6 weeks. LFTs returned to normal in all patients. In both groups of patients from the European phase III trial, (Gleolan® and placebo control), 1 patient developed a hepatic serious adverse event (SAE). The Gleolan® patient developed cholelithiasis.

Patients will be continuously monitored for sustained Grade 3 or 4 elevations in their LFTs at six weeks following Gleolan® administration. A comprehensive metabolic serum panel, including albumin, alkaline phosphatase, total bilirubin, bicarbonate, BUN, calcium, chloride, creatinine, glucose, potassium, total protein, SGOT[AST], SGPT[ALT], sodium, gamma glutamyltranspeptidase (GGT), will be obtained prior to surgery, within 48 hours of surgery, 2 weeks, and 6 weeks after surgery. These tests will only be repeated after 6 weeks if SGOT[AST], SGPT[ALT], and gamma glutamyltranspeptidase (GGT) remain elevated after 5-ALA dosing.

We will continuously monitor the rate of sustained Grade 3 or 4 elevations in LFTs at 6 weeks following Gleolan® administration and accrual will be halted if there is sufficient evidence that the sustained Grade 3 or 4 LFT elevation rate exceeds the acceptable rate of 5% by more than 5% (unacceptable rate 10%). If the cumulative number of patients that experience grade 3 or 4 elevations in the LFTs at 6 weeks from drug administration is greater than the associated boundary value $b_{\mbox{\tiny K}}$ listed in the table below, among the k patients enrolled in the trial, enrollment in the trial will be halted for safety considerations prompting IRB notification and a DSMB meeting will be requested.

# of accrued	2-9	10-20	21-23
subjects, k			
Boundary, b _k	1	2	3

The following table shows the probability of early stopping if the true rates of sustained grade 3 or 4 elevations in the LFTs are at or lower than 10%. For safety of the participants, we would like to have a low probability of early stopping if the sustained LFT rates are low, but high probability of early stopping if the sustained LFT rate is high.

Probability of early stop based on true grade 3 or 4 LFT rate					
True SAE rate	5%	6.2%	7.5%	8.8%	10%
Probability of early stop	0.15	0.21	0.28	0.36	0.44

This stopping rule was computed using the toxbdry function in R and calculations of this function are based on methods described in Chapter 12 of Jennison and Turnbull³⁹ and in the illustrative paper by Ivanova, Qaquish and Schell⁴⁰.

toxbdry(0.05,0.10,c(1:23),cP0=0.15,cP1=0.30,ngrid=5)

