In a comparative, unblinded phase-III European trial (MC-ALS.3/GLI), 201 patients with malignant gliomas received 5-ALA HCI (20 mg/kg body weight). 176 of these underwent fluorescence-guided resection with subsequent radiotherapy. 173 patients received standard resection (without 5-ALA administration) and subsequent radiotherapy. With a follow-up of at least 180 days after administration, 2/201 (1.0 %) drug recipients experienced side effects (mild vomiting 48 hours after surgery and mild photosensitivity 48 hours after study surgery). A patient accidentally received an overdose of the medicinal product (3000 mg instead of 1580 mg) which was well tolerated. Respiratory insufficiency resolved completely with ventilation. A more pronounced asymptomatic transient increase of liver enzymes was observed in 5-ALA HCI recipients, peaking between 7 and 14 days. Increased levels of amylase, total bilirubin, and leukocytes, but decreased levels of platelets and erythrocytes were observed, but differences between treatment groups were not statistically significant.

Liver toxicity (from phase III European trial) as elevated liver function tests (LFTs) occurred in over 10% of patients after oral 5-ALA, anesthesia, and fluorescence-guided tumor resection. LFT changes included increased alanine aminotransferase (ALT), aspartate aminotransferase (AST), gamma glutamyltransferase (GGT) and blood amylase at 24 h, 7 d, and 6 weeks after 5- ALA ingestion. Approximately, 10% had Grade 3 or 4 elevations in GGT at 7 days; 5% had Grade 3 or 4 elevations in GGT at 6 weeks, and 1% had persistent ALT or AST at 6 weeks. **LFTs returned to normal in all patients.** In both groups of patients from the European phase III trial, (5-ALA and placebo control), 1 patient developed a hepatic serious adverse event (SAE). The 5-ALA patient developed cholelithiasis.

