4.2 Toxicities and Dosing Delays/Dose Modifications

Any patient who receives treatment on this protocol will be evaluable for toxicity. Each patient will be assessed for the development of toxicity according to the Time and Events table (See section 5.4). Toxicity will be assessed according to the NCI Common Toxicity Criteria for Adverse Events (CTCAE), version 4.0. Dose adjustments should be made according to the system showing the greatest degree of toxicity.

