4.6 Duration of Follow Up

Analysis of progression and correlative studies will be performed as per standard of care for 6 weeks post-surgery. Follow-up will consist of 3 time points: within 48h post-surgery, a 2 week and a 6 week postoperative office visit. Patients removed from treatment for unacceptable adverse events will be followed until resolution or stabilization of the adverse event.

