4.7 Removal of Patients from Protocol Therapy

Patients will be removed from therapy when any of the criteria listed in Section 5.5 apply. Notify the Principal Investigator, and document the reason for study removal and the date the patient was removed in the Case Report Form. The patient should be followed-up per protocol.

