5.5 Removal of Subjects from Study

Patients can be taken off the study treatment and/or study at any time at their own request, or they may be withdrawn at the discretion of the investigator for safety, behavioral or administrative reasons. The reason(s) for discontinuation will be documented and may include:

- 5.5.1 Patient voluntarily withdraws from treatment (follow-up permitted);
- 5.5.2 Patient withdraws consent (termination of treatment and follow-up);

- 5.5.3 Patient is unable to comply with protocol requirements;
- 5.5.4 Patient demonstrates disease progression (unless continued treatment with study drug is deemed appropriate at the discretion of the investigator);
- 5.5.5 Patient experiences toxicity that makes continuation in the protocol unsafe;
- 5.5.6 Treating physician judges continuation on the study would not be in the patient's best interest:
- 5.5.7 Patient becomes pregnant (pregnancy to be reported along same timelines as a serious adverse event);
- 5.5.8 Development of second malignancy (except for basal cell carcinoma or squamous cell carcinoma of the skin) that requires treatment, which would interfere with this study;
- 5.5.9 Lost to follow-up. If a subject cannot be located to document status after a period of 2 months postoperatively, the subject will be considered lost to follow-up. All attempts to contact the subject during this time period will be documented.

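### Section 6.5 ends study participation after a serious reaction to the single dose without keeping safety follow-up, in conflict with 4.2 and 4.7; read literally, it omits scheduled liver tests in a dosed patient (minor)

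*Combined protocol and SAP*

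**What the plan says.** Section 6.5 opens with a rule for the individual patient: "If patients exhibit respiratory distress or serious allergic reaction following 5-ALA administration, their participation in the study will cease". It does not refer to the sections on removal or follow-up.

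Other sections bear on the same patient:

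- **4.2:** "Any patient who receives treatment on this protocol will be evaluable for toxicity". Its next sentence ties that toxicity assessment to the Time and Events table in 5.4, which lists laboratory panels within 48 h of surgery, at week 2 and at week 6.
- **4.7 with 5.5:** a patient who meets any 5.5 criterion is removed from therapy, and "The patient should be followed-up per protocol". Criterion 5.5.5 reads: "Patient experiences toxicity that makes continuation in the protocol unsafe".
- **4.5:** an allergic reaction before surgery ends the therapy protocol and the fluorescence-guided surgery. Follow-up is not mentioned.
- **4.6:** "Patients removed from treatment for unacceptable adverse events will be followed until resolution or stabilization of the adverse event". Section 6.1 likewise monitors a patient with an adverse event until it resolves or reaches another stated end.
- **1.2.3**, on the European phase III trial: "A more pronounced asymptomatic transient increase of liver enzymes was observed in 5-ALA HCI recipients, peaking between 7 and 14 days".

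**The concern.** Treatment is one oral dose. When a reaction follows it, no dosing is left to stop. Participation can then mean only the fluorescence-guided procedure and follow-up, and after the procedure only follow-up. Taken at its word, 6.5 releases a fully exposed patient who has just reacted badly from the adverse-event and LFT assessments that 4.2 and 4.7 require.

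Sections 4.6 and 6.1 do not fill this gap. They follow a known event to its end, and an acute reaction may settle well before the visits at issue. The liver-enzyme rise is a different event. The protocol describes it as asymptomatic, peaking at 7 to 14 days and possible up to 6 weeks, so scheduled blood tests are the only dependable way to find it. The 48 h panel comes too early for that peak.

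**Working it through.** **1. The sections side by side, for a dosed patient with a serious allergic reaction**

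| Section | What ends | Scheduled LFT follow-up |
|---|---|---|
| 6.5, opening sentence | study participation | no exception made |
| 4.2 | nothing | required for every treated patient |
| 4.7 with 5.5.5 | therapy | continues per protocol |
| 4.5 (reaction before surgery) | therapy and fluorescence-guided surgery | silent |
| 4.6, 6.1 | not stated | only the known event is followed |

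Section 4.5 is silent, so it does not conflict with 6.5. Sections 4.2 and 4.7 do.

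**2. Assessments at risk.** The 5.4 table has three post-dose panels: 48 h, week 2 and week 6. If participation ends after the 48 h visit, two are omitted. If it ends on day 0, all three are.

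**3. What a missed panel could hide.** The cited 6-week figures are 5% for Grade 3 or 4 GGT and 1% for persistent ALT or AST elevation (1.2.3 and 6.5). Applying them to a patient who has reacted is an assumption. Section 6.5 also states: "Approximately 10% had Grade 3 or 4 elevations in GGT at 7 days". No panel is scheduled at day 7, so that figure cannot be tied to a lost visit. The documents give no week-2 rate.

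**4. How often.** The protocol gives no rate for these reactions. The four studies in 1.2.3 that report recipient numbers cover 21 + 21 + 36 + 201 = 279 people, some at lower doses. No serious allergic reaction is listed. One respiratory event appears, next to an accidental overdose: "Respiratory insufficiency resolved completely with ventilation". The text does not attribute it to 5-ALA. Counting it anyway, for illustration:

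- Rate r = 1/279 = 0.36%, exact 95% upper limit 2.0% (1.98% unrounded).
- Expected among 23: 23 × r = 0.08 (upper 0.46).
- Chance of at least one: 1 − (1 − r)^23 = 8% (upper 37%).
- Expected Grade 3 or 4 GGT elevations missed at 6 weeks in the whole trial: 0.08 × 0.05 = 0.004 (upper 0.46 × 0.05 = 0.023).

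**5. The LFT stopping rule.** Inputs from 6.5: halt when the cumulative count exceeds 1 for k = 2–9, 2 for k = 10–20 and 3 for k = 21–23. The method is an exact binomial recursion over the 23 patients. The protocol prints stop probabilities of 0.15 at a true rate of 5% and 0.44 at 10%. The printed boundaries give 0.112 and 0.384, so the plan's own figures do not reproduce. That is a separate matter, and only differences are used here.

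| Scenario | True 5% | True 10% |
|---|---|---|
| All LFTs kept | 0.112 | 0.384 |
| Each patient unobservable with probability 1/279; event probability p(1 − r) | 0.112 (loss 0.1 points) | 0.382 (loss 0.2 points) |
| Same, at the upper-limit rate | 0.108 (loss 0.4 points) | 0.372 (loss 1.2 points) |
| Exactly one such patient, kept in k, mean over positions | 0.103 (range 0.097–0.112) | 0.358 (range 0.348–0.379) |

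If the patient were replaced under 4.8 and dropped from k, there would be no loss.

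**The case against.** The strongest reply is that the rest of the protocol already answers the question. Section 4.2 puts every treated patient on the assessment schedule without exception. A later paragraph of 6.5 itself plans LFT monitoring to six weeks after administration and excludes nobody. Section 5.5 ends follow-up expressly only when consent is withdrawn (5.5.2), and 4.7 says to follow removed patients. On this view 6.5 uses loose wording for ending therapy.

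Much of that stands. It probably reflects the intent, and it gives a site a sound basis for continuing follow-up. A reader might infer that the LFTs will be lost; the documents support only that they are at risk. The conflict remains, because 5.5 itself separates leaving treatment from leaving the study, and 6.5 uses the wider term with no cross-reference.

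Further points on that side also hold. The protocol says LFTs returned to normal in all patients of the European trial. The 2-week and 6-week visits are also regular post-surgical examinations (5.3.1), so clinical contact need not end when surgery goes ahead. Neither point secures the LFT panel.

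Three other strong readings are tempting and unsupported:

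- **A 10% chance of a missed Grade 3 or 4 elevation.** That figure belongs to day 7, when no panel is planned.
- **Biased adverse-event rates or sensitivity.** No direction of bias is shown, and nothing in the documents links these reactions to LFT elevation.
- **An unrecorded reaction.** Sections 6.1, 6.2.1 and 6.4.1 still require it to be monitored, recorded and, if serious, reported.

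**Conclusion.** The conflict is real and minor. Section 6.5, followed literally, would omit the week-2 and week-6 adverse-event and LFT assessments in a dosed patient after a serious reaction, and the 48 h panel too if participation ends on day 0. It matters for that patient's safety. At trial level the effect on the stopping rule is negligible. That conclusion rests on an assumed reaction rate, since the protocol states none, and on a single respiratory event that may not be drug-related. The 6-week liver figures come from glioma patients and are assumed to carry over.

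**What to change.** In 6.5, replace the closing clause of the opening sentence, which ends participation, with: *protocol therapy and fluorescence-guided surgery will cease; per 4.2 and 4.7, the 48 h, 2-week and 6-week adverse-event and LFT assessments continue unless the patient withdraws consent (5.5.2), dated from dosing if surgery does not take place.*

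The dating clause is needed because the visits are timed from surgery, while the LFT stopping rule counts from drug administration.

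The cost is one sentence. The visits and tests are already in the 5.4 schedule. The downside is a few follow-up visits in patients whose fluorescence procedure was cancelled.

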2.3.2.2 Incidence of Gleolan®-related adverse events

3.0 PATIENT ELIGIBILITY

3.1 Inclusion Criteria

- 3.1.1 Subjects included in this trial must have had documentation of a new or recurrent head and neck or skull base tumor for which surgical resection is indicated and has been planned. These patients will include those with newly diagnosed or recurrent malignancies.
- 3.1.2 Age 18-80
- 3.1.3 Karnofsky score >60%
- 3.1.4 Subjects must have normal organ and marrow function as defined below:

- leukocytes ≥ 3,000/mcL - absolute neutrophil count ≥ 1,500/mcL - platelets ≥ 100.000/mcl

- total bilirubin within normal institutional limits

- AST(SGOT)/ALT(SPGT) \leq 2.5 X institutional upper limit of normal

- creatinine within normal institutional limits

OR

Creatinine clearance >60 mL/min/1.73m2 for patients with creatinine levels above institutional normal as defined per institution.

- 3.1.5 The effects of Gleolan® (5-ALA) on the developing human fetus are unknown. For this reason, women of child-bearing potential and men must agree to use adequate contraception (hormonal or barrier method of birth control; abstinence) prior to study entry and for the duration of study participation. A pregnancy test will be performed for all women of childbearing ability prior to surgery (see Exclusion Criteria below). Should a woman become pregnant or suspect she is pregnant while participating in this study, she should inform her treating physician immediately.
- 3.1.6 Ability to understand and the willingness to sign a written informed consent.

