5.1.10 Serum chemistries

Comprehensive metabolic panel (CMP) to include: albumin, alkaline phosphatase, ALT/SGPT, AST/SGOT, BUN, creatinine, electrolytes (sodium, potassium, calcium, chloride, bicarbonate), glucose, and total bilirubin.

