5.4 Time and Events Table

Study Assessment or Procedure	Baseline (-60 to day 0 before surgery)	Day 0 (At 5-ALA administr ation)	Day 0 (prior to surgery)	Within 48h of surgery	Week 2	Week 6
Informed Consent	X					
Demographics and Medical History	Х			X	Х	Х
Physical Exam (vitals, weight, Karnofsky status)	Х	X		X	Х	Х
Concurrent Medications	Х	Х	Х	Х	Х	Х
Adverse Events Evaluation	Х	Х	Х	Х	Х	Х
Tumor Imaging	Х					
Pregnancy test ^d	Х					
Other labs (CMP, CBC, GGT) ^{a,b,c}	Х			Х	Х	Х
Gleolan® (5- ALA) ^e		X				

- a. Albumin, alkaline phosphatase, total bilirubin, bicarbonate, BUN, calcium, chloride, creatinine, glucose, potassium, total protein, SCOT (AST), SCPT (ALT), sodium, gamma glutamyl transpeptidase (GGT)
- b. Phosphorus, uric acid, creatinine kinase, and amylase will be added as clinically necessary/indicated.
- c. Repeat only those labs that remain abnormal after 6 weeks unless attributed to other therapy
- d. Pregnancy test (women of childbearing potential)- part of standard pre-operative protocol
- e. Gleolan® (5-ALA) is dosed as 20mg/kg. Oral administration is one-time only and based on actual weight on day of surgery.

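### The LFT halting boundary in 6.5 has no baseline reference, so a grade 3-4 GGT present before dosing and unchanged at week 6 counts as an event

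*Combined protocol and SAP*

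**What the plan says.** - **Monitored quantity (6.5).** "We will continuously monitor the rate of sustained Grade 3 or 4 elevations in LFTs at 6 weeks following Gleolan® administration". The acceptable rate is 5% and the unacceptable rate 10%.
- **Counting sentence (6.5).** It opens "If the cumulative number of patients that experience grade 3 or 4 elevations in the LFTs at 6 weeks from drug administration". Once that count exceeds the tabulated limit, enrollment stops, the IRB is notified and a DSMB meeting is requested. The boundary is 1 for 2-9 patients, 2 for 10-20 and 3 for 21-23. This sentence contains neither *sustained* nor any pre-dose comparison.
- **Enzymes (6.5).** ALT, AST and GGT are the three tests discussed. Grade 3 and grade 4 are described as more than 5-10 times and more than 10 times the upper limit of normal.
- **Eligibility (3.1.4).** "total bilirubin within normal institutional limits", and AST/ALT no more than 2.5 times the upper limit. No GGT limit is set.
- **Reporting (6.4.2).** For a subject with raised GGT at entry and normal ALT and AST, "reporting will not be required unless the grade has increased by 2 levels".
- **Sampling (5.4 and 6.5).** GGT is scheduled for every patient before surgery, within 48 hours, at 2 weeks and at 6 weeks. The screening list in 5.1.10 ("albumin, alkaline phosphatase, ALT/SGPT, AST/SGOT, BUN, creatinine" and others) does not include it.

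**The concern.** The boundary is meant to detect liver enzyme elevation following the drug. For AST and ALT an absolute grade at week 6 serves that purpose, because the eligibility cap of 2.5 times the upper limit keeps grade 3-4 values out at entry. GGT has no such cap. A patient may enter at grade 3, stay at grade 3, and be counted although nothing changed after dosing.

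The protocol foresees patients with raised entry GGT. Section 6.4.2 judges them relative to baseline, while 6.5 judges them on absolute grade, and nothing reconciles the two.

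With boundaries of 1, 2 and 3, a single such patient uses up much of the allowance. What is at stake is an enrollment halt, with IRB notification and a DSMB request, in a 23-patient pilot for a reason unrelated to the drug.

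**Working it through.** **Inputs.** From 6.5: boundary b = 1 (k = 2-9), 2 (k = 10-20), 3 (k = 21-23); halt when the count exceeds b, so at 2, 3 or 4 events; rates 5% and 10%. From 8.2: n = 23. Assumed: patients are independent and each week-6 result is known in enrollment order. The number or prevalence of pre-existing cases is not in the documents.

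**Method.** Exact binomial recursion, one patient at a time, absorbing when the count exceeds b.

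**The plan's own figures first.**

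| True rate | 5% | 6.2% | 7.5% | 8.8% | 10% |
|---|---|---|---|---|---|
| Printed in 6.5 | 0.15 | 0.21 | 0.28 | 0.36 | 0.44 |
| Recomputed from printed boundary | 0.112 | 0.170 | 0.239 | 0.314 | 0.384 |

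The printed probabilities do not reproduce; the recomputed values are 4 to 6 points lower. That is a separate matter, to be checked against the software output. The comparisons below all use the printed boundary, so both sides are on the same footing.

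**No pre-existing case, 5% rate.** By patient 9, P(2 or more of 9) = 1 − 0.95⁹ − 9(0.05)(0.95⁸) = 0.071. Carried to patient 23, the halt probability is 0.112.

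**One pre-existing case among patients 1-9, 5% for the rest.**
- By patient 9, one event among the other 8 is enough: 1 − 0.95⁸ = 0.337.
- Otherwise (0.663), 2 or more of patients 10-20 are needed: 1 − 0.95¹¹ − 11(0.05)(0.95¹⁰) = 0.102, which adds 0.663 × 0.102 = 0.068.
- Patients 21-23 add about 0.002. The total is 0.406.

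**By position of the one case, 5% for the rest.** Patients 1-9: 0.406. Patients 10-20: 0.248. Patients 21-23: 0.127. The average over positions is (9 × 0.406 + 11 × 0.248 + 3 × 0.127)/23 = 0.294. The same average at a 10% on-study rate is 0.612, against 0.384 without the case.

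**By assumed prevalence q, 5% on-study rate.** Counted rate = 1 − 0.95(1 − q).

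| q (assumed) | Counted rate | Halt probability |
|---|---|---|
| 0 | 5.0% | 0.112 |
| 1% | 5.95% | 0.157 |
| 2% | 6.9% | 0.206 |
| 5% | 9.75% | 0.369 |
| 10% | 14.5% | 0.627 |

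**The case against.** *The rule says sustained elevations following administration.* It does, repeatedly. But the term is undefined and absent from the counting sentence, and an enzyme at grade 3 before dosing and again at week 6 is sustained in the ordinary sense. The word does not settle the baseline question.

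*The 5% may already include background.* Section 6.5 cites 5% with grade 3-4 GGT at 6 weeks in the European phase III trial and does not say whether this was adjusted for baseline. If it was not, an absolute count compares like with like and the inflation above is an upper reading. This stands in part. It is weakened by the same section, which describes transient increases after administration and says liver tests returned to normal in all patients. That reads as a post-dose effect.

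*A halt is not termination.* Correct. The IRB and DSMB would have the scheduled baseline GGT before them, so a false halt is likely to cost time, not the trial.

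*A reader might go further* and infer from 6.4.2 that a real worsening, such as GGT grade 2 to grade 3, could escape the count. The documents do not support this. Section 6.4.2 is a reporting rule that never mentions the boundary. Its waiver needs raised entry GGT, normal ALT and AST, and a rise of fewer than two grades. Week-6 GGT is scheduled for everyone, and 6.2.1 requires all adverse events to be recorded. On the wording of 6.5 that patient is a boundary event. The only residue is that the source of the count is not named.

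*Footnote c of the 5.4 table* ("Repeat only those labs that remain abnormal after 6 weeks unless attributed to other therapy") might be read as a competing attribution rule. It governs repeat testing after week 6, not event counting.

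**Conclusion.** The point holds for pre-existing GGT elevation. As worded, 6.5 counts an unchanged pre-dose grade 3-4 GGT as an event, and one such patient among 23 raises the halt probability at the acceptable 5% rate from 0.11 to about 0.29, with a range of 0.13 to 0.41 by position.

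This rests on the printed boundary, independence, results known in enrollment order, and the 5% being an on-study rate without background. The single-patient figure needs no prevalence assumption but does suppose that such a patient enrolls. The prevalence table is illustration only. The absence of GGT from 5.1.10 is editorial, since 5.4 and 6.5 both require it before surgery.

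**What to change.** Reconcile 6.5 with 6.4.2:

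1. Define the boundary event relative to baseline, as a post-dose worsening from the patient's pre-dose grade. The clinical threshold is for the sponsor to set. Name the pre-dose panel that serves as reference, since the baseline window in 5.4 runs up to 60 days.
2. Define *sustained* and use it in the counting sentence, or remove it throughout.
3. State that the count comes from the scheduled week-6 panels, not from reports under 6.4.2.
4. Confirm whether the 5% and 10% rates are total or baseline-referenced, so that the rates and the event are on one basis.
5. As an editorial alignment, add GGT to 5.1.10.

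The cost is protocol wording; no new samples are needed. If the rates are confirmed as baseline-referenced, the boundary can stay as designed on this point.

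The downside is that a patient already at a high GGT grade who stays there no longer counts. If 5% and 10% are total rates, the rule becomes less sensitive. With an assumed q of 2%, a 10% total rate leaves 1 − 0.90/0.98 = 8.2% countable, and the halt probability falls from 0.384 to 0.277. Item 4 should therefore be settled before the boundary is kept.
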